9.10 Conversion Factors

To convert days into weeks, months or years the following conversion factors will be used:

- 1 week = 7 days
- 1 month = 30.4375 days
- 1 year = 365.25 days

9.11 Date of Last Contact

The date of last contact will be derived for participants not known to have died at the analysis cut-off or database lock using the latest complete date prior to or at the data cut-off or database lock date among the following:

- Date of last AE start date
- Date of last blood sample
- Date of last ECG or vital sign assessment
- Date of last temperature or malaria signs and symptoms assessment

Only dates associated with actual examinations of the participant reported in the eCRF will be used in the derivation. Dates associated with a technical operation unrelated to participant status such as the date a blood sample was processed will not be used.

9.12 Definition of On-treatment Period

The on-treatment period is defined as the time from the date of first dose of study intervention to the date of premature study termination, cut-off or database lock date or death, whichever occurs first.

9.13 Imputation of Missing Data

No action will be taken to handle missing data. A participant who withdraws prior to the last planned observation in a study period will be included in the analyses up to the time of discontinuation.

Unless otherwise specified, all data will be evaluated as observed, and no imputation method for missing values will be used.

In order to determine treatment-emergent AEs, incomplete AE-related start dates will be imputed as follows:

- In case the onset date is missing completely or missing partially but the onset month and year, or the onset year are equal to the start of study intervention then the onset date will be imputed by the minimum of start of study intervention and AE resolution date (if not missing). If AE resolution date is completely or partially missing, the study intervention date will be used.
- In all other cases, the missing onset day or missing onset month will be imputed by 1.

Incomplete or missing stop dates will not be imputed, since no durations of AEs are planned to be derived.

Missing or partially missing dates for Medical History will not be imputed.

In order to allocate medications to either previous or concomitant, the following imputation rules for (partially) missing start dates will be applied:

- If the day is missing, it will be imputed by the 1st day of the month.
- If both day and month are missing the date will be imputed by 1st January.
- If the date is completely missing, no imputation will be performed.

10 Study Participants

The subsections in this section include specifications for reporting participant disposition and study intervention/study discontinuations. Additionally, procedures for reporting protocol deviations are provided.

10.1 Disposition of Participants and Discontinuations

The following will be presented in a summary table:

- Total number of participants screened (i.e., participants who gave informed consent)
- Number of screened participants who discontinued from the trial prior to randomization
 - Participant did not meet all eligibility criteria
 - Withdrew consent
 - Progressive disease
 - Lost to follow-up
 - Death
 - Other
- Number of randomized participants
- Number of randomized participants who did not receive treatment (as applicable)
- Number of treated participants
- Number and percentage of treated participants who completed study
- Number and percentage of treated participants who discontinued the study, with the primary reason of discontinuation by treatment and overall

A frequency table displaying the number of participants of the different Analysis Sets will be provided in addition.

10.2 Protocol Deviations / Exclusion from Analysis Sets

10.2.1 Important Protocol Deviations

Important protocol deviations will be identified for all participants by either site monitoring, medical review processes or programming and confirmed prior to or at the Data Review Meeting at the latest.

Any important protocol deviation is documented in SDTM datasets whether identified through site monitoring, medical review or programming. The management of protocol deviations is outside of this IAP document.

A frequency table as well as a listing of important protocol deviations, will be provided based on the FAS.

10.2.2 Reasons Leading to the Exclusion from an Analysis Set

A frequency table organized according to reason for exclusion from the PK analysis set, as well as a listing, will be provided.

11 Demographics and Other Baseline Characteristics

11.1 Demographics

Descriptive statistics will be presented for age, adolescent status, sex, ethnicity, and race. Adolescent status is defined by age ≥ 12 to < 18 years.

11.2 Medical History

The medical history will be summarized from the “Medical History” eCRF page, using MedDRA version 27.1, preferred term as event category and system organ class (SOC) body term as Body System category. Each participant will be counted only once within each PT or SOC.

Medical history will be displayed in terms of frequency tables: ordered by primary SOC and PT in alphabetical order.

11.3 Other Baseline Characteristics

Summary and frequency tables, as applicable, will be provided for ECG results (number of participants with abnormal ECG findings and summary statistics of ECG results for participants with abnormal findings), height, weight, BMI, vital signs and laboratory results.

12 Previous or Concomitant Therapies/Procedures

Previous medications are defined as any medication discontinued prior to the administration of study intervention. If the date values do not allow a medication to be classified as previous

medication (e.g. due to missing dates which are not imputed; see Section 9.13), the medication will be considered as a concomitant medication.

Concomitant medications are defined as any medication taken during the course of the study, with a starting date greater than or equal to the administration of study intervention, or with a starting date prior to the administration of study intervention and ongoing at the time of the administration of study intervention.

The World Health Organization Drug dictionary (WHO-DD) version effective at the date of database lock will be used for coding of prior and concomitant medications and they will be described using Preferred Term (PT) as applicable.

Previous and concomitant medications will be listed. Concomitant procedures, if any, will also be listed.

A frequency table of previous and concomitant medications will be provided by ATC level 2 and PTs sorted by ATC and PTs in alphabetical order.

13 Study Intervention: Compliance and Exposure

M5717+pyronaridine will be administered once as single dose on Day 1, when the participants are hospitalized. Thus, compliance for the combination is not applicable.

Malarone is given at three consecutive days starting at Day 1 in hospital. The last dose on Day 3 has to be taken by the participants at home. Compliance, though, is not assessed.

A frequency table displaying intake of study treatment, reasons for not taking study treatment and number of participants with different dose combinations of M5717 and pyronaridine will be provided.

14 Efficacy Analyses

14.1 Primary Estimand

For the description of the attributes of the primary estimand please refer to the Clinical Study Protocol, Section 3.

14.1.1 Primary Objective: Derivation and Analysis of the Primary Estimand

The primary endpoint is defined as the time (in days) to first recorded parasitemia (parasite count >0) since the first negative blood smear (parasite count of 0) after treatment (followed at least by 1 subsequent visit with a negative blood film), i.e. the time without a positive blood smear. For the endpoint assessment it is irrelevant whether the recurrent parasite detected after treatment is genetically the same strain present at baseline or a new one. Participants who never had a negative blood smear after treatment are not considered for this analysis of time to repositivation.

In order to derive the population-level summary of the estimand related to time to parasitemia, different intercurrent events (ICE) have to be considered. ICE as defined by the study protocol will be identified and handled as described in the following:

- **Intake of rescue medication:** filtering concomitant medications programmatically for all artemisinin based combination therapies (artemether-lumefantrine, artesunate-amodiaquine, dihydroartemisinin-piperaquine, artesunate-sulphadoxine-pyremethamine), chloroquine, quinine, halofantrine, primaquine and by medical review. A composite variable strategy is applied, i.e. the primary endpoint is considered as failure (= positive blood smear at the time of rescue medication intake).
- **Intake of antibiotics or prohibited concomitant medication with an antimalarial effect:** filtering concomitant medications programmatically for sulphadoxine-trimethoprim, doxycycline, quinolone antibiotics including fluoroquinolones, azithromycin, erythromycin and all other macrolides and by medical review. An on-treatment strategy is applied, i.e. time to parasitemia is censored at the time of antibiotics or prohibited medication intake.
- **Experience of any event that affects absorption, e.g. vomiting within the first 24 hours after dosing:** filter AE data programmatically for preferred term (PT) "Vomiting" within the System Organ Class (SOC) "Gastrointestinal disorders" and by medical review. A treatment policy strategy is applied, i.e. treatment effect is estimated regardless of ICE.
- **Death due to malaria or other reasons:** filter SAEs programmatically for fatal events with outcome "death" and by medical/safety review. Death cases for which the primary reason is ticked as "progressive disease and/or disease-related condition" qualify as death due to malaria. A composite variable strategy is applied if the death was due to malaria (i.e. a parasitemia event is considered at the time of death) and an on-treatment strategy is defined if death was due to other reasons (i.e. time to parasitemia is censored at the time of death)

The population-level summary is defined as the Hazard Ratios (HRs) for each dose of M5717 relative to the untreated participants in Cohort 4. HRs are estimated from a Cox Proportional Hazards Model with time to parasitemia included as the dependent variable and dose cohorts, site and sex included as independent factors, and baseline age, body weight and parasite density included as independent covariates. Participants will be censored in case of occurrence of an ICE as described above, at the last available visit in case of premature study discontinuation or at the end of study in case no parasitemia event was observed.

For the multivariable (primary) model, a table showing HRs together with 95% Wald CIs will be provided which will contain in addition estimates of coefficients, SEs and p-values (based on Likelihood Ratio Test) in order to assess whether the factors and covariates included into the model have a significant influence on the time to parasitemia. As additional information a table providing information on censoring frequency and occurrence of ICEs will be provided.

As part of descriptive analyses of the primary endpoint, which also covers the analysis of the second estimand (incidence of parasitemia), a table displaying number and percentages of

parasitemia events (estimated directly from the data) will be provided together with estimates of a Kaplan-Meier (KM) analysis. Median time of protection and 95% CI will be estimated using the KM method for each cohort. As a graphical illustration, a KM-figure will be provided showing time to parasitemia in days after parasite clearance.

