Visit Number	Prescreening	Scr + Visit 1 ^a	Visit 2 ^a	Visit 3	Visit 4	Visits 5 to 12	Visit 13	Unscheduled Visit	
^a Visit 1 and 2: Participants randomized to Cohorts 1 to 3 will remain in hospital or stay in the vicinity of the sites for 24 hours for PK sampling and assessment of parasitemia (see Table 2).
 
Participants randomized to Cohort 4, will visit the clinic on Days 1, 2, and 3 for dosing in an outpatient setting
	
Timepoint	Prescreening	Day 1	Day 2	Day 3	Day 4	Week 2 to 9 (weekly visits starting at Day 8)	EOS (last visit) Week 10, Day 64 ^b	Can be required due to AEs, and AESIs; follow-up of AEs and AESIs	
^b Day 64 or day of completion or premature discontinuation.
 
Participants will remain in the study until parasitemia or until Day 64, whichever comes first.
 
All EOS evaluations will be completed before providing antimalarial rescue treatment if required.
	
Blood films (microscopy)		X	X	X	X	X	X		
Thick and thin blood films will be collected at Visit 1 (predose) to confirm eligibility and at all visits.
 
Cohorts 1 to 3: The exact timepoints on Days 1 to 2 are provided in Table 2.
 
Cohort 4: Blood films should be examined at Screening, predose on Day 1, Day 2, and Day 3.
 
Blood sampling for parasitemia will be done simultaneously with PK.
	
Inclusion/ exclusion criteria		X								
COVID-19 antigen test		X							
The test will be conducted at Visit 1. Additional COVID-19 tests may be conducted as needed.
	
Demographic and medical history		X								
Randomization		X								

Assessments & Procedures	Outpatient	Outpatient/Inpatient ^a		Outpatient					Notes	
Visit Number	Prescreening	Scr + Visit 1 ^a	Visit 2 ^a	Visit 3	Visit 4	Visits 5 to 12	Visit 13	Unscheduled Visit	
^a Visit 1 and 2: Participants randomized to Cohorts 1 to 3 will remain in hospital or stay in the vicinity of the sites for 24 hours for PK sampling and assessment of parasitemia (see Table 2).
 
Participants randomized to Cohort 4, will visit the clinic on Days 1, 2, and 3 for dosing in an outpatient setting
	

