Table 2 Pharmacokinetics and Blood Films: Sampling Timepoints on Days 1 and 2 – Cohorts 1 to 3

Assessment									Notes
Visit	1							2	
Day	1							2	For subsequent PK blood sampling for M5717 and pyronaridine refer to Table 1
Window		± 5min	± 10 min	± 20 min	± 30 min	± 30 min	± 60 min	± 120 min	
Hours after M5717 + pyronaridine dose	Pre	1h	2h	4h	6h	8h	12h	24h	
PK blood sampling for M5717	X	X	X	X	X	X	X	X	Not applicable for Cohort 4.
PK blood sampling for pyronaridine	X	X	X	X	X	X	X	X	Not applicable for Cohort 4.
Blood films (microscopy)	X	X			X		X	X	Not applicable for Cohort 4.

PK = pharmacokinetic(s).

2 Introduction

M5717 is a first-in-class NCE targeting the *Plasmodium* cytosolic protein synthesis “Elongation Factor 2” for the treatment and prevention of malaria due to the activity in the liver and blood stage of the parasite life cycle.

Pyronaridine tetraphosphate is an antimalarial drug marketed in combination with artesunate as Pyramax for which the CHMP adopted a positive scientific opinion in accordance with Art 58 of (EC) Regulation 726/2004 on 16 February 2012. Pyronaridine is a drug that interferes with the digestive system of *P. falciparum* and *P. berghei* and inhibits the production of complexes with β -hematin to enhance hematin-induced human blood cell lysis (Croft 2012).

M5717 and pyronaridine are intended to be developed as a fixed-dose combination for either the treatment of acute uncomplicated malaria or for the prevention of symptomatic malaria in populations living in endemic areas. The initial step of the clinical development plan of the combination is to generate initial safety, efficacy, and exposure data in symptomatic malaria patients and asymptomatic, malaria-infected individuals through the conduct of 2 Phase 2a PoC studies (CAPTURE-1 and CAPTURE-2) to prioritize the final indication for Phase 2b and Phase 3.

There is a clear need to accelerate the development of dedicated drug combinations for malaria prevention. A reduction of >50% of malaria cases was observed in regions where malaria preventive treatments were systematically applied (Cairns 2012) leading to a significant reduction in mortality in the population. WHO has recently published new treatment policies to reinforce the use of chemoprevention (WHO Guidelines for Malaria, 2022), which combined with the increasing development of resistance against the 2 main standards of care, highlights the need for dedicated new therapies.

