Individuals who were randomized to Cohorts 1 to 4 of the main study will be approached to identify if they are willing to be involved in this substudy. Participation in this substudy is entirely voluntary. A participant's decision to participate or to not participate in the substudy will not affect their participation, care, or treatment in the main study.

Participants are eligible to be included in the substudy if in addition to the eligibility criteria of the main study (see [Section 5.1](#) and [5.2](#)) all of the following criteria apply.

Inclusion criteria:

1. *P. falciparum* gametocyte carriage confirmed by microscopy with a minimum gametocyte density of 2 per 500 WBC (~32 per μ L) at the time of randomization in the main and substudy

Exclusion criteria:

1. Administration of immunoglobulin and/or any blood products within the 3 months preceding the study participation
2. Any finding that would in the Investigator's opinion interfere with study participation

Objectives and Endpoints of the Substudy

Mosquito infectivity will be assessed at 3 levels: the mean number of oocysts in a sample of mosquitoes (i.e. oocyst density), the proportion of mosquitoes in a given assay infected with any number of oocysts (i.e. mosquito infection rate), and the relation between infectivity of the study participants and infectivity of mosquitoes. These different aspects of mosquito infectivity are translated into primary and secondary/CCI as described in below table. All analyses of mosquito infectivity will be conducted on all participants who are infectious at baseline (i.e. with a minimum gametocyte density of 2 per 500 WBC (~32 per μ L at randomization).

Objectives	Estimands/Endpoints	Ref. #
Primary		
To assess the intra-individual reduction of infectivity of gametocytes (in terms of mosquito infection rate) following administration of Malarone alone or M5717 plus pyronaridine (single dose regimen) at Day 2 (24 hours) compared to pretreatment (Day 1)	
Endpoint: Percent reduction in the mosquito infection rate of mosquitoes fed with Day 2 (24 hours post treatment) blood sample and mosquitoes fed with Day 1 (pretreatment) blood sample. The mosquito infection rate is defined by the proportion of mosquitoes in an assay infected with any number of oocysts.
 
Population-level summary: Arithmetic mean by dose cohort with 95% CI
	S1
Secondary		

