14.2.3 Parasite Clearance Time

For estimating parasite clearance time (in hours), which is the time from dosing (first dose in the Malarone treatment cohort) to the first negative blood film (parasite count of 0 on microscopy), followed at least by 1 subsequent visit with a negative blood film. Patients should not be considered for analysis if they did not have parasites >0 at any timepoint. The same ICEs as defined in Section 5 will be considered. The median parasite clearance time will be estimated by use of Kaplan-Meier method for each cohort. Participants will be censored in case of occurrence of an ICE if the ICE occurred before the first negative blood film, at the last available visit in case of premature study discontinuation before the first negative blood film or at the end of study in case no parasite clearance event was observed.

15 Safety Analyses

This section includes specifications for summarizing safety endpoints that are common across clinical studies such as adverse events, laboratory tests and vital signs.

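### Clearance is confirmed by a later visit, not by later films, so a chance-negative Day 1 film in Cohorts 1 to 3 can turn the clearing baseline infection into a same-day parasitemia event

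*SAP*

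**What the plan says.** **Primary rule (SAP 14.1.1).** The event is "first recorded parasitemia (parasite count >0) since the first negative blood smear (parasite count of 0) after treatment (followed at least by 1 subsequent visit". The first negative smear counts as clearance if at least one subsequent visit also has a negative film. The SAP does not say whether that means the next visit or any later one. Strain does not matter: it is "irrelevant whether the recurrent parasite detected after treatment is genetically the same strain present at baseline or a new one".

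**Clearance time (SAP 14.2.3).** The same condition is used: "followed at least by 1 subsequent visit with a negative blood film".

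**Film schedule.** Protocol Table 2, "Pharmacokinetics and Blood Films: Sampling Timepoints on Days 1 and 2 – Cohorts 1 to 3", places films predose and at 1, 6 and 12 h in Visit 1, and at 24 h in Visit 2. Table 2 does not apply to Cohort 4. For that cohort Table 1 states: "Cohort 4: Blood films should be examined at Screening, predose on Day 1, Day 2, and Day 3". Cohort 4 therefore has one film per visit after dosing begins and none later on Day 1. All cohorts have films at Day 3, Day 4 and the weekly visits.

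**Entry density (Protocol 5.1, criterion 2).** 40 to 10,000 asexual parasites/µL.

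**The concern.** A confirmation rule should stop a single chance-negative film from being taken as clearance. Here the confirming unit is a visit, while Cohorts 1 to 3 have three post-dose films inside Visit 1. A positive film between the first negative and the confirming visit does not cancel the clearance; it becomes the event.

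Parasites left from the baseline infection would then count as loss of protection on Day 1. Because only Cohorts 1 to 3 have several post-dose films in one visit, the error is unequal between arms and works against M5717 plus pyronaridine. It also shortens parasite clearance time, in the extreme to 1 h. The study is meant to inform the dosing interval (Protocol 4.2), and few true events are expected in the top-dose arm, so a small number of false ones matters.

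**Working it through.** **1. Applying the rule to film sequences (negative = 0, positive = +)**

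| Cohort and films | Confirmed by next visit | Confirmed by any later visit | Film-level rule (see fix) |
|---|---|---|---|
| 1-3: 1 h 0, 6 h +, 12 h +, 24 h 0, then 0 | clock 1 h, event 6 h | clock 1 h, event 6 h | clock 24 h, no event |
| 1-3: 1 h +, 6 h 0, 12 h +, 24 h 0, then 0 | clock 6 h, event 12 h | clock 6 h, event 12 h | clock 24 h, no event |
| 1-3: 1 h 0, 6 h +, 12 h +, 24 h +, 48 h 0, then 0 | clock 48 h, no event | clock 1 h, event 6 h | clock 48 h, no event |
| 1-3: 1 h +, 6 h +, 12 h 0, then 0 | clock 12 h, no event | clock 12 h, no event | clock 12 h, no event |
| 4: Day 2 0, Day 3 +, Day 4 0, then 0 | clock Day 4, no event | clock Day 2, event Day 3 | clock Day 4, no event |

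The first two rows fail under either reading. The fourth shows that genuine clearance is unaffected by the fix. Since time is in days with the +1 convention (SAP 9.9), such an event is stored as day 1.

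**2. Looking for a safeguard elsewhere.** SAP 9.3 drops repeated and unscheduled values, but the Day 1 films are scheduled. Strain is ignored, so genotyping does not remove the event from the primary analysis. The only sensitivity analysis (SAP 14.1.2) concerns absorption. Protocol 9.4.1.1 gives no film-level rule.

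**3. Chance that a film misses parasites.** Protocol Appendix 2 equates 2 per 500 white cells with about 32/µL, which implies 32 × 500 / 2 = 8,000 white cells/µL. With Poisson counting, P(0) = exp(−density × cells read / 8,000). The number of cells read for asexual counts is not given, so 200 to 1,000 is assumed.

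| Density | 200 read | 500 read | 1,000 read |
|---|---|---|---|
| 40/µL | 37% | 8% | 0.7% |
| 80/µL | 14% | 0.7% | <0.1% |
| 400/µL | about 0 | about 0 | about 0 |

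**4. Frequency of false events.** Simulation of 400,000 participants. Assumptions not in the documents: log-uniform entry density over 40-10,000/µL, a lag of 0-12 h before decline, a fall of 2-4 log10 per 48 h, Poisson counting. Films at 1, 6, 12, 24, 48, 72 and 168 h (Cohorts 1 to 3) or 24, 48, 72 and 168 h (Cohort 4).

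| Cells read | Cohorts 1-3, next visit | Cohort 4, next visit | Cohorts 1-3, film-level rule |
|---|---|---|---|
| 200 | about 4-6% | at most about 0.15% | at most about 0.45% |
| 500 | 0.4-2.4% | at most about 0.15% | at most about 0.45% |
| 1,000 | under 1% | at most about 0.15% | at most about 0.45% |

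**5. Effect on the hazard ratio.** The plan's own figure first (Protocol 9.2: HR 0.29, 21 events, 80% power, α = 0.05). Schoenfeld, two-sided: 4 × (1.960 + 0.842)² / (ln 0.29)² = 20.5, so 21 events; power at 21 events is 0.81. It reproduces. The stated 63% and 87% free of parasitemia give ln(0.87)/ln(0.63) = 0.30, used below. True events expected in the top-dose arm: 45 × 0.13 = 5.9.

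With a fraction f of false events in that arm and none in Cohort 4, HR ≈ ln(0.87 × (1 − f)) / ln(0.63):

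- f = 1%: 0.32
- f = 2%: 0.35
- f = 5%: 0.41

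As a check, a simulated two-arm Cox model (45 per arm, weekly detection, 800 runs) gave a median HR of 0.29 with no false event, 0.34 with one and 0.41 with two. The 95% CI excluded 1 in 77%, 66% and 52% of runs. Two of 45 is 4.4%, a rate that under the next-visit reading arises only near 200 cells read.

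**The case against.** The strongest reply is that the size rests on assumptions. The only counting basis in the documents is 500 white cells, and that is for gametocytes in the substudy. At 1,000 cells under the next-visit reading the problem nearly vanishes. The analysis is descriptive (Protocol 9.1), and the bias runs against the investigational arms, so it cannot manufacture a benefit. A Day 1 event in someone followed to Day 64 would also be visible in the listings. All of this stands and limits the weight of the point. It does not repair the rule: the SAP gives no basis for overriding an event that its own definition produces.

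Four stronger readings are tempting and are not supported:

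- **Scored as a new infection.** The primary endpoint ignores strain; it records parasitemia only.
- **Gametocyte-only films count as events.** A parasite count above 0 could be read that way, but the documents treat gametocytemia separately (its own row in Protocol Table 1; Protocol 8.1 and 9.4.1.2). The substudy criterion, "gametocyte carriage confirmed by microscopy with a minimum gametocyte density of 2 per 500 WBC", selects among people already randomized to the main study, so it does not enrich the primary analysis set with carriers.
- **A hazard ratio of 0.41 as the expected result.** That needs about 5% false events, hence about 200 cells read or the loose any-later-visit reading. The loose reading gives up to about 13% in the same simulation, but it leaves the confirmation clause almost empty and is unlikely to be what was meant.
- **Primary time zero must move to the daily films.** That is a design preference. The film-level rule already removes the traced artefact.

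**Conclusion.** The rule is wrong as written in SAP 14.1.1 and 14.2.3. A chance-negative Day 1 film, a later positive Day 1 film and a negative 24 h film together produce a same-day event under either reading of the visit clause. If the next visit is meant, the artefact is essentially confined to Cohorts 1 to 3, biases the hazard ratio toward 1 and shortens clearance time.

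The film sequences follow from the text alone; the frequencies do not. They depend on the assumed density distribution, clearance speed and cells read, and concern mainly participants with low or nearly cleared counts. A realistic shift is from 0.30 to about 0.32-0.35 for false events in 1-2% of the top-dose arm, with larger shifts only at the unfavourable end. This should be corrected, but it does not undermine the study.

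**What to change.** In SAP 14.1.1 and 14.2.3:

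1. Define clearance as the first negative film for which every later scheduled film of that visit, and the film or films of the next scheduled visit, are also negative. State *next* visit, not any later visit.
2. Count parasitemia events only after clearance so defined.
3. Add a sensitivity analysis of the primary endpoint that takes time zero only from time points common to all four cohorts.
4. Optionally, add the word asexual to the count definition, to match inclusion criterion 2.

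The cost is SAP wording and programming; every film needed is already scheduled. Time zero moves later by up to about a day for affected participants.
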